RESEARCH PROTOCOL

A RANDOMIZED CONTROLLED TRIAL TO COMPARE HYDROMORPHONE VS FENTANYL IN CHILDREN UNDERGOING TONSILLECTOMY SURGERY

[name]
Clinical Research Coordinator, Anesthesiology
[contact]

[name]
Professor, Otolaryngology
[contact]

[name]
CA3 Resident, Anesthesiology
[contact]

[name], PhD
Assistant Professor, Pediatric Anesthesiology
[contact]

Original Version: January 22, 2020

Revision: February 12, 2020

Revision: March 26, 2020

CONFIDENTIAL: This document is the intellectual property of [name] and [name], PhD. Acceptance of this document constitutes the agreement by the recipient that no unpublished information contained herein will be published or disclosed without prior written approval.

SYNOPSIS

Objective - To compare hydromorphone versus fentanyl for pain control following tonsillectomy or adenotonsillectomy surgery.

Study Period - 2 years

Number of Patients - 300 pediatric patients presenting for tonsillectomy or adenotonsillectomy at St. Louis Children's Hospital (SLCH)

Study Treatment - Hydromorphone vs fentanyl dosed per study design

Study Design - This is a randomized clinical trial with masked assessment, comparing recovery indices for patients receiving intermediate acting versus short acting opioid analgesia using hydromorphone or fentanyl as intraoperative analgesics. An otherwise standardized anesthetic and analgesic regimen will be utilized, consistent with routine care at SLCH. Patients will be randomized 1:1 in blocks of 4 within strata. Patients will be randomized to receive either hydromorphone or fentanyl throughout the perioperative period by opening a sealed protocol envelope.

Inclusion Criteria

1. Children ages 2 to 15 years old
2. Presenting for tonsillectomy or adenotonsillectomy surgery
3. American Society of Anesthesiologists Physical Status (ASAPS) Classification 1, 2 or 3
4. Provide Informed Consent / Assent (as appropriate)

Exclusion Criteria

1. Additional Concurrent surgeries, exclusive of myringotomy tubes, minor oral/nasal procedures (e.g. frenulectomy), and endoscopic procedures
2. Revision tonsillectomy or revision adenotonsillectomy surgery
3. Known pregnancy
4. Any condition which would make the participant, in the opinion of the investigator or the attending anesthesiologist caring for the patient, unsuitable for the study.

Measurements - We will compare the incidence of administration of analgesic rescue medication in the post-operative recovery area. We will also compare post-operative pain scores and the amount of opioid pain medications administered to patients postoperatively expressed in morphine equivalents. Optional opioid plasma concentrations will be measured at three time points using mass spectroscopy. Additionally, we will compare the rates of post-operative respiratory complications, PONV, and length of PACU stay between patients administered fentanyl vs. hydromorphone. Finally, we will assess patient and family satisfaction with treatment through a survey sent on POD 3 as well as validated NIH PROMIS questionnaires.

CONFIDENTIAL: This document is the intellectual property of [name] and [name], PhD. Acceptance of this document constitutes the agreement by the recipient that no unpublished information contained herein will be published or disclosed without prior written approval.

Outcomes - Perioperative analgesic efficacy and side effect comparisons between hydromorphone and fentanyl in children undergoing tonsillectomy surgery.

CONFIDENTIAL: This document is the intellectual property of [name] and [name], PhD. Acceptance of this document constitutes the agreement by the recipient that no unpublished information contained herein will be published or disclosed without prior written approval.

1. Introduction

1.1. Study Abstract: Every year hundreds of children undergo tonsillectomy surgery at St. Louis Children's Hospital (SLCH) and many of these children experience significant postoperative pain. Severe postoperative pain can delay recovery and hospital discharge if it impedes eating and drinking. This pain can also lead to significant patient and parental anxiety, and may worsen patient anxiety for future health care related experiences. Opioids are commonly used to treat severe pain; however, opioids also have attendant side effects such as sedation, postoperative respiratory depression (e.g. apnea), and nausea and vomiting. Fentanyl and hydromorphone are the primary opioids used at SLCH in the operating theater and the immediate postoperative period. Fentanyl has a shorter duration of action than hydromorphone and is often chosen in the belief that using the shortest-acting opioid will reduce the risks of sedation and apnea. However, there is limited evidence to suggest that this is the case. Interestingly nurses in the SLCH Post Anesthesia Care Unit have noted a subjective difference in pain levels in patients receiving hydromorphone versus fentanyl with the perception that patients administered hydromorphone, on average, require fewer doses of rescue opioid analgesics. In addition, a recently completed prospective study of fentanyl vs. hydromorphone for pain control in patients undergoing eye muscle surgery suggests that hydromorphone provides both lower pain ratings and faster PACU recovery. Our goal is to determine whether there is a difference in post-operative outcomes between patients receiving fentanyl or hydromorphone post tonsillectomy.

1.2. Research Questions

1.2.1. Is there a difference in the rate of administration for rescue opioid analgesic medications in children undergoing tonsillectomy who are administered hydromorphone as compared to fentanyl perioperatively?

1.2.2. Is there a difference in the postoperative pain score in children undergoing tonsillectomy who are administered hydromorphone as compared to fentanyl perioperatively?

1.2.3. Is there a difference in the cumulative morphine equivalents administered postoperatively in children undergoing tonsillectomy who are administered hydromorphone as compared to fentanyl perioperatively?

1.2.4. Is there a difference in post anesthesia care unit length of stay in children undergoing tonsillectomy who are administered hydromorphone as compared to fentanyl perioperatively?

1.2.5. Is there a difference in nausea or the number of vomiting episodes postoperatively and 72 hours after discharge in children undergoing tonsillectomy who are administered hydromorphone as compared to fentanyl perioperatively?

CONFIDENTIAL: This document is the intellectual property of [name] and [name], PhD. Acceptance of this document constitutes the agreement by the recipient that no unpublished information contained herein will be published or disclosed without prior written approval.

1.2.6. Is there a difference in pain scores reported by the parent 72 hours after discharge in children undergoing tonsillectomy who are administered hydromorphone as compared to fentanyl perioperatively?

1.2.7. Is there a difference in the number of desaturation events, defined as $\text{SPO}_2 < 90\%$ for 2 minutes or less than 85% for 1 minute, postoperatively in children undergoing tonsillectomy who are administered hydromorphone as compared to fentanyl perioperatively?

1.2.8. Is there a difference in the number of witnessed apneic events postoperatively or at 72 hours after discharge in children undergoing tonsillectomy who are administered hydromorphone as compared to fentanyl perioperatively?

1.2.9. Is there a difference in patient and family satisfaction with care between children undergoing tonsillectomy who are administered hydromorphone as compared to fentanyl perioperatively?

1.3. Purpose of the Study Protocol. The proposed project will test whether there is a difference in multiple metrics of pain between patients who receive hydromorphone or those who receive fentanyl during tonsillectomy. The results of this study should inform the way anesthesiologists approach the treatment of pain following the most common pediatric surgical procedure at SLCH, and in the United States. If a difference is found, appropriate dissemination of findings could influence the universal approach taken for pain control in the most common pediatric surgery.

2. Background

2.1. Prior Literature and Studies. Tonsillectomy is the most common pediatric operation performed in the United States, with more than 500,000 tonsillectomies performed annually¹. The primary indication for tonsillectomy is childhood obstructive sleep apnea (OSA), defined by periodic, partial or complete obstruction of the upper airway during sleep. OSA is a common disorder in pediatric patients, with a prevalence of 1-3%². It is as common as childhood asthma and children with OSA often require tonsillectomy surgery to correct their OSA². As mentioned, the treatment of OSA is the primary indication for more than 75% of children undergoing tonsillectomy with or without adenoidectomy³. Unfortunately, children at high risk for OSA are three times more likely to have post-tonsillectomy respiratory complications and apneic adverse events than children at low risk for OSA^{4,5} and the rate of complications in patients with OSA post-tonsillectomy (16 –27%) is substantially increased compared to that of the general pediatric post-operative population (0 –1.3%)⁶⁻¹⁰. These complications include oxygen desaturation, hypercapnia, obstructive apneas requiring CPAP or airway instrumentation, unexpected ICU admission, and in rare cases, death. Concerns for a heightened risk of opioid induced respiratory depression make the peri-operative use of opioids in children with OSA particularly challenging and controversial.

CONFIDENTIAL: This document is the intellectual property of [name] and [name], PhD. Acceptance of this document constitutes the agreement by the recipient that no unpublished information contained herein will be published or disclosed without prior written approval.

There is currently not a standard of practice for pain management for tonsillectomy surgery at SLCH. Published guidelines recommend decreasing opioid doses in all patients with sleep apnea, for fear of respiratory depression, however they do not give recommendations regarding the use of short vs. intermediate acting opioids¹¹. The nurses in the SLCH PACU have subjectively noted a decreased need for opioid rescue analgesia when hydromorphone is administered intraoperatively as compared to fentanyl. Additionally, a recently completed prospective study of fentanyl versus hydromorphone for pain control in patients undergoing eye muscle surgery at SLCH suggests that hydromorphone results in lower pain scores and faster PACU recovery¹². There are limited data comparing different opioids in pediatric tonsillectomy surgery published in the literature. As far as we are aware, this will be the first randomized controlled trial comparing the intermediate acting opioid hydromorphone to the shorter acting opioid fentanyl for this patient population.

2.2. Rationale for the Study. Providing safe and effective pain control is important for these patients. Subjective observations indicate that hydromorphone may provide superior pain control as compared to fentanyl. This hypothesis has not been rigorously tested. We aim to ameliorate this deficit.

3. Study Objectives

3.1. Primary Aim. The **primary aim** of our study is to compare the need for rescue opioid analgesic medication between patients receiving fentanyl and hydromorphone following adenotonsillectomy surgery. We will also compare post-operative pain scores between the two groups, and the amount of opioid pain medications administered to patients postoperatively expressed in morphine equivalents. Patients will be randomized 1:1 in the operating room to receive either fentanyl or hydromorphone during the perioperative period. We hypothesize that compared to fentanyl, the use of hydromorphone will result in lower need for rescue opioid analgesic in post-surgical recovery.

3.2. Secondary Aims. The **secondary aims** of our study are to compare pain scores, the rates of post-operative respiratory complications, PONV, and length of PACU stay between patients administered fentanyl vs. hydromorphone. We hypothesize that there will be no differences between patients who receive fentanyl and those who receive hydromorphone.

3.3. Rationale for Selection of Outcome Measures. These are the primary concerns for care of patients following tonsillectomy surgery. Nearly all patients will have postoperative pain, and many will experience some degree of postoperative nausea and vomiting. Respiratory complications are possible after emergence from a general anesthetic, especially after the use of opioids in the perioperative setting, and especially after tonsillectomy surgery.

CONFIDENTIAL: This document is the intellectual property of [name] and [name], PhD. Acceptance of this document constitutes the agreement by the recipient that no unpublished information contained herein will be published or disclosed without prior written approval.

4. Study Design

4.1. Overview. This is a randomized clinical trial with masked assessment, comparing recovery indices for patients receiving longer acting versus shorter acting opioid analgesia using hydromorphone or fentanyl as intraoperative analgesics. An otherwise standardized anesthetic and analgesic regimen will be utilized, as consistent with routine care at SLCH.

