4.3. Exclusion Criteria

- 4.3.1. Additional Concurrent surgeries, exclusive of myringotomy tubes, minor oral/nasal procedures (e.g. frenulectomy), and endoscopic procedures
- 4.3.2. Revision tonsillectomy or revision adenotonsillectomy surgery
- 4.3.3. Known pregnancy
- 4.3.4. Any condition which would make the participant, in the opinion of the investigator, unsuitable for the study

4.4. Ethical Considerations. All patients will receive pain medication as well as medication to control for postoperative nausea and vomiting as per routine care at SLCH. The attending anesthesiologist will accompany the child to the PACU, and rescue drugs will be available if additional pain medication is needed or if there is concern for respiratory distress. Both medications (hydromorphone and fentanyl) to be compared are standard of care analgesics at SLCH and on formulary.

4.5. Risks and Benefits. We do not know if patients will benefit from the intervention. For future patients, it is anticipated that investigators may be able to determine whether one of the pain medications has a better potential to reduce the need for rescue analgesia without a concomitant increase in side effect following tonsillectomy surgery. There is a possibility that parents may feel uncomfortable answering some items on the questionnaires.

4.6. Early Withdrawal of Subjects. Patients may be withdrawn from the study if during surgery an additional procedure is required or if the lead study physician ([name]) determines it is not in the best interest of the patient to continue in the study. Caregivers may decide to withdraw their child from the study at any time without penalty. Withdrawn children will be replaced with a new subject to maintain a consistent number of enrolled patients in each group.

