connected to the patient as per standard of care. Patients will be randomized to receive either hydromorphone or fentanyl in the operating room determined by opening a sealed protocol envelope. Administration and dosing of the randomized opioid to each case will be under the direction of the primary anesthesia team under the direction of the pediatric anesthesiologist caring for the child. In addition to the randomized opioid, patients will receive non-opioid analgesics and PONV prophylaxis as per routine care at SLCH. Blinding will be achieved using syringes prepared by SLCH investigational pharmacy.

4.7.4 Optional opioid Plasma Concentration Assessments. Approximately 3 mls of whole blood will be collected from patients at three time points: 1) within 10 minutes of administration of study drug, 2) within 10 minutes of PACU arrival, and 3) within 10 minutes of PACU discharge. Blood samples will be collected through an additional IV line placed in the surgical suite after anesthesia is given. Opioid (hydromorphone or fentanyl) blood levels will be measured using mass spectrometry. This type of analysis does not require *apriori* knowledge of the medication administered and will maintain the masking protocol. A Population Pharmacokinetic Analysis will be performed. The patient may decline to participate in the blood draw component of the study and remain in the study for data collection relating to the primary endpoint. Additionally, failed or missed blood draws in individual patients will not adversely affect the population analysis.

4.8. Treatment Regimen. Patients will receive a general anesthetic as per the standard of care at SLCH. Analgesia will include opioids and non-opioid adjuvants for pain in addition to anti-emetics per routine care at SLCH. Airway maintenance will be via an endotracheal tube supervised by the anesthesiologist responsible for the care of the patient in the operating room.

4.9. Method for Assigning Subjects to Treatment Groups. Patients will be randomized to either hydromorphone or fentanyl in the preoperative area prior to presenting to the operating room by investigational pharmacy staff. Randomization will be 1:1 in blocks of 4 within strata. Stratification will be done by age group (2-7, 8-12, and 13-15), and OSA diagnosed using sleep polysomnography within the last year.

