After transferring from Phase I recovery, a member of the research team will continue to evaluate patient's pain using the same scale on arrival and before discharge. The patient's level of pain (rFLACC) and need for any additional analgesic medications will also be evaluated. rFLACC is standard of care at SLCH and all personnel are well versed in its application. After discharge, the patient will receive a telephone call or text at 24 hours after surgery to evaluate post-operative nausea and vomiting and the level of pain at home. The need for additional pain medication will also be assessed. This is standard of care at SLCH and performed for all patients who are discharged the day of surgery, regardless of type of surgery. Respiratory events will be assessed initially using SpO₂ monitoring immediately after arrival to the PACU, followed by clinical assessment after PACU discharge. Postoperative nausea and vomiting is assessed using observation and patient verbalization.

CONFIDENTIAL: This document is the intellectual property of [name] and [name], PhD. Acceptance of this document constitutes the agreement by the recipient that no unpublished information contained herein will be published or disclosed without prior written approval.

Patient and family satisfaction with care will be assessed using a survey on postoperative day 3, as well as the validated NIH PROMIS questionnaires for Pediatric Self-Report (ages 8-17) and Parent Proxy Report (ages 5-17). We will use the following NIH PROMIS questionnaires: Pain Behavior, Pain Interference, and Pain Quality. PROMIS questionnaires will be sent to patients via e-mail through the REDCap server on postoperative day 7 (\pm 1 day).

5.4. Safety and Compliance Monitoring. All patients will be monitored by an anesthesiologist for the first 5 minutes in the PACU and then every 5 minutes by a registered nurse until discharged from the PACU to the Same Day Surgery unit. Monitoring is continuous until the patient recovers from anesthesia and then every 5 minutes x3, then every 15 minutes until PACU discharge. The same tool, the rFLACC, is used throughout the hospitalization to assess pain. Postoperative nausea and vomiting is assessed using observation and patient verbalization.

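### PONV is compared without recording postoperative antiemetic doses, so treatment could mask a difference in vomiting counts and nobody could tell

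*Combined protocol and SAP*

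**What the plan says.** The PONV outcome is described in three places.

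- Section 1.2.5 asks: "Is there a difference in nausea or the number of vomiting episodes postoperatively and 72 hours after discharge".
- Section 3.2 (Secondary Aims) sets out to "compare pain scores, the rates of post-operative respiratory complications, PONV, and length of PACU stay", and then states: "We hypothesize that there will be no differences between patients who receive fentanyl and those who receive hydromorphone". It gives no case definition of PONV and no margin.
- Sections 5.3 and 5.4 describe ascertainment: "Postoperative nausea and vomiting is assessed using observation and patient verbalization". After discharge, 5.3 says that "the patient will receive a telephone call or text at 24 hours after surgery to evaluate post-operative nausea and vomiting".

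Antiemetics appear only as routine care. Section 4.4 says: "All patients will receive pain medication as well as medication to control for postoperative nausea and vomiting as per routine care at SLCH". Section 4.7.3 says that "patients will receive non-opioid analgesics and PONV prophylaxis as per routine care at SLCH", and 4.8 likewise mentions anti-emetics as routine. No section lists a postoperative antiemetic dose as a collected variable, a component of PONV or an adjustment.

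**The concern.** A vomiting count is measured after treatment has had a chance to act on it. A child treated after a first episode may have fewer later ones. If one opioid causes more emesis, more children in that arm will probably be treated, and more of their later episodes prevented. Masked syringes (4.7.3) do not remove this, because the treatment responds to symptoms and not to knowledge of the arm. The trial could then report similar vomiting counts while antiemetic use differed, and the data would not show it.

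There is a second, smaller route. Eligibility starts at age 2 (4.2.1), and the youngest children may not be able to say that they feel sick. A child treated on suspicion, with no symptom written down and no later vomiting, could be recorded as free of PONV.

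The plan handles pain differently: need for rescue opioid is the primary aim (3.1), and postoperative opioid is totalled in morphine equivalents (1.2.3). Section 1.1 names nausea and vomiting among the opioid side effects, yet PONV has no corresponding treatment measure.

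**Working it through.** The plan gives no PONV rate, effect size, margin or power, so there is no figure of its own to reproduce. All rates below are assumptions that show how the mechanisms behave. Only the 150 per arm (300 patients, 1:1) comes from the protocol (6.1).

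**Vomiting counts**

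Let episodes without rescue be Poisson with mean L. The chance of at least one episode is P = 1 − exp(−L). If rescue after the first episode prevents a fraction e of later ones, in both arms alike, the observed mean is P + (1 − e)(L − P).

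- L = 0.4: P = 0.330. With e = 0.8, the observed mean is 0.330 + 0.2 × 0.070 = 0.344.
- L = 0.6: P = 0.451. With e = 0.8, it is 0.451 + 0.2 × 0.149 = 0.481.
- L = 1.0: P = 0.632. With e = 0.8, it is 0.632 + 0.2 × 0.368 = 0.706.

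| Assumed means | True difference | Observed, e = 0.8 | Observed, e = 0.5 |
|---|---|---|---|
| 0.4 v 0.6 | 0.20 | 0.137 (31% lost) | 0.161 (20% lost) |
| 0.6 v 1.0 | 0.40 | 0.225 (44% lost) | 0.290 (27% lost) |

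The ratio of means shrinks too. With e = 0.8, 0.6/0.4 = 1.50 becomes 0.481/0.344 = 1.40, and 1.0/0.6 = 1.67 becomes 0.706/0.481 = 1.47. In this model the shrinkage is general: the slope of observed on true mean is 1 − e(1 − exp(−L)), which is below 1 for any e above 0.

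**PONV incidence**

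Assume true rates of 30% v 20% and let a share m of cases go unrecorded, so that the observed rate is p(1 − m). Power is for a pooled two-sided 5% test with n = 150 per arm:

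Φ{[d√n − 1.96√(2p̄(1 − p̄))] / √(p₁(1 − p₁) + p₂(1 − p₂))}

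Here d is the difference in rates and p̄ their average. With no misses: (1.225 − 1.200)/0.608 = 0.04, giving power of 52%.

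| Missed, higher arm / lower arm | Observed rates | Difference (points) | Risk ratio | Power |
|---|---|---|---|---|
| 0 / 0 | 30% v 20% | 10 | 1.5 | 52% |
| 10% / 10% | 27% v 18% | 9 | 1.5 | 46% |
| 30% / 30% | 21% v 14% | 7 | 1.5 | 36% |
| 50% / 50% | 15% v 10% | 5 | 1.5 | 26% |
| 40% / 10% | 18% v 18% | 0 | 1.0 | none |
| 10% / 40% | 27% v 12% | 15 | 2.25 | 91% |

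Equal misses reduce the absolute difference and the power but leave the risk ratio alone. Unequal misses can erase the difference or enlarge it. The documents do not say which children would be missed, so no row can be preferred.

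**The case against.** A reader might infer that treated children are undercounted as PONV cases, and that the comparison is therefore pushed toward the absence of differences hypothesized in 3.2. The documents do not support that.

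- A child treated because vomiting was seen or nausea was reported already has an event under 1.2.5. Rescue cannot erase the first episode. Incidence is lost only when a child is treated with no symptom recorded, and no section says that this happens.
- Observation is a stated route of ascertainment alongside what the child says, so nausea in a child who cannot speak of it is not necessarily lost.
- The incidence table shows that the effect of misses can run either way.
- The documents do not say how often, or on what threshold, a non-prophylactic antiemetic is given. The rescue drugs in 4.4 are for pain and respiratory distress.
- Power in the illustration is only 52% with perfect measurement. The trial was sized on rescue opioid (6.1), so most of that weakness is not caused by the PONV definition.
- A composite has its own error. If 5% of unaffected children received a dose without true PONV, 20% v 30% would become 0.20 + 0.05 × 0.80 = 24.0% v 0.30 + 0.05 × 0.70 = 33.5%. The difference falls to 9.5 points and the ratio to about 1.40, even though the error is the same in both arms.

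All of this stands. It rules out a claim of directional bias in PONV incidence and is a good reason not to replace the symptom outcomes. It does not answer the point about counts: if rescue prevents later episodes, the count difference can shrink, and the plan collects nothing that would reveal it.

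**Conclusion.** The concern holds in a limited form. The plan does not say that postoperative non-prophylactic antiemetic use will be recorded, so a difference in vomiting counts can be attenuated by treatment without anyone being able to detect or bound it. Some children treated without a recorded symptom may also be missed.

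The losses of 20% to 44% in the count difference depend on assumed Poisson means, assumed prevention of 50% to 80% of later episodes, and the same response to rescue in both arms. They show what is possible and do not estimate what will happen in this trial. For PONV incidence, neither size nor direction is established.

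Nor can attenuation be said to confirm the hypothesis in 3.2. No margin is stated, so a non-significant result would not establish absence of a difference under any definition of PONV. This is a cheap improvement to one secondary outcome and does not touch the primary comparison.

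**What to change.** Add to 1.2.5 and 3.2, with a matching line in 6.2:

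1. Abstract every non-prophylactic antiemetic dose given after surgery, with its time, from the medication record. Keep intraoperative prophylaxis as a separate variable.
2. Compare by arm the proportion of children given such a dose, and report it beside the vomiting counts.
3. Prespecify an in-hospital PONV composite as a supporting or sensitivity analysis: at least one of observed vomiting or retching, stated nausea, or a non-prophylactic antiemetic dose. Retain the nausea and vomiting-count outcomes of 1.2.5 as they are.

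Antiemetic care does not change. The cost is a sentence or two of protocol text and a little abstraction work. The downside is that doses given without true PONV would slightly dilute the composite, which is why it belongs beside the symptom outcomes and not in their place. It covers only the in-hospital part of 1.2.5. For the rest, the 72-hour window there and the 24-hour contact in 5.3 need to be reconciled separately.

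### Section 5.3 describes no contact that collects the parent pain score, nausea and vomiting, and witnessed apneas that questions 1.2.5, 1.2.6 and 1.2.8 ask for at 72 hours after discharge

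*Combined protocol and SAP*

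**What the plan says.** Three of the nine research questions in section 1.2 look beyond the hospital stay to 72 hours:

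- 1.2.5 concerns "nausea or the number of vomiting episodes postoperatively and 72 hours after discharge".
- 1.2.6 asks: "Is there a difference in pain scores reported by the parent 72 hours after discharge in children undergoing tonsillectomy".
- 1.2.8 concerns the "number of witnessed apneic events postoperatively or at 72 hours after discharge".

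Section 5.3 (Schedule of Measurements) describes three contacts after the child goes home:

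- **24 hours.** In the plan's words, "the patient will receive a telephone call or text at 24 hours after surgery to evaluate post-operative nausea and vomiting". The contact also covers pain at home and the need for more analgesia. It is presented as routine care, "performed for all patients who are discharged the day of surgery".
- **POD 3.** "Patient and family satisfaction with care will be assessed using a survey on postoperative day 3". The synopsis says the same: "we will assess patient and family satisfaction with treatment through a survey sent on POD 3". Neither place gives the survey any other content.
- **Day 7, plus or minus 1 day.** PROMIS questionnaires in three pain domains, with parent proxy forms starting at age 5.

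Respiratory events are followed by SpO₂ on arrival in the PACU, "followed by clinical assessment after PACU discharge". No time, assessor or caregiver item is attached to that later assessment.

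**The concern.** Each research question should lead to a scheduled measurement of the right quantity at the right time. For the 72-hour parts of these three questions the link is missing: the questions name outcomes and a time, and the schedule names no contact that measures those outcomes then.

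Two things are at stake. First, if 5.3 is carried out as written, 1.2.6 and the 72-hour parts of 1.2.5 and 1.2.8 end without data. Pain and nausea/vomiting could then be reported only at some other time, chosen afterwards. Apnea at home could not be reported from any listed contact. Caregiver counts that nobody asked for at the time cannot be reliably rebuilt later. Second, apnea matters here: section 1.1 says fentanyl is often preferred in the belief that it lowers the risk of sedation and apnea, and that the evidence for this is limited.

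**Working it through.** **Inputs.** The outcomes and times come from 1.2.5, 1.2.6 and 1.2.8, and the contacts from 5.3. Two inputs are assumptions:

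- d, the hours from surgery to discharge from hospital, is not in the documents. I take 4 to 24 hours.
- POD 3 is treated as about 3 × 24 = 72 hours after surgery.

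The plan gives no figure of its own to reproduce.

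**Step 1: items against contacts.**

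| Item wanted at 72 h after discharge | 24-hour call or text | POD 3 survey | PROMIS, day 7 (±1) |
|---|---|---|---|
| Parent pain score (1.2.6) | Pain at home, but earlier; reporter and scale not named | Not listed | Pain domains, but later; parent form from age 5, while the trial enrolls from age 2 |
| Nausea (1.2.5) | Yes, but earlier | Not listed | No |
| Number of vomiting episodes (1.2.5) | Vomiting, but no count mentioned; earlier | Not listed | No |
| Number of witnessed apneas (1.2.8) | Not listed | Not listed | No |

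Items described as collected near 72 hours: 0 of 4. Post-discharge contacts that mention apnea: 0 of 3.

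**Step 2: other sections.** Section 5.4 covers monitoring in hospital. Section 5.6 relies on data gathered in routine care. Section 10.1 is general adverse event monitoring. None adds a 72-hour item.

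**Step 3: how much of each question is touched.** Question 1.2.6 depends wholly on the 72-hour collection. Questions 1.2.5 and 1.2.8 depend on it in part, since both also ask about the postoperative period, for which 5.3 does describe assessment. So 3 of 9 questions are touched: 1 entirely and 2 in part.

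**Step 4: the clock.** Measured from surgery, the requested time is d + 72 hours and the survey falls at about 72 hours.

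- Offset = (d + 72) − 72 = d.
- At d = 4: 76 − 72 = 4 hours.
- At d = 24: 96 − 72 = 24 hours.

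The phrase could instead mean the whole 72 hours following discharge. The survey could then look back over 72 − d of those hours: 68/72 = 94% at d = 4 and 48/72 = 67% at d = 24. The offset is small for a short stay and grows for a child kept overnight.

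**The case against.** The strongest reply is that a contact at about the right time already exists. The POD 3 survey goes out close to 72 hours, its items are not reproduced, and a plan may describe a survey by its main purpose without listing every question. This stands. The documents show that the collection is not described; they do not show that it will not happen. A reader might infer that these data will never be collected, and the documents do not support that.

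Two other strong readings also fail.

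- **Measuring the gap from the 24-hour call.** That call precedes the requested time by (d + 72) − 24 = d + 48 hours, or 52 to 72 hours on the assumed range, which looks dramatic. But 5.3 does not offer the call as the 72-hour contact. The fair comparison is with POD 3, where the offset is about d.
- **Saying that three of nine questions cannot be answered.** The in-hospital parts of 1.2.5 and 1.2.8 are covered by the assessments in 5.3, so only 1.2.6 is at risk as a whole.

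It can also be said that none of this touches the main result. That is correct. The primary aim is rescue opioid use in recovery, and the section 3.2 aims name no 72-hour time point.

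What the reply leaves unanswered is that the questions specify four items and a time, while both descriptions of the survey mention only satisfaction. Even if the items are on the form, the two clocks still disagree.

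**Conclusion.** The point holds as a mismatch between the stated questions and the stated schedule. As written, 5.3 describes no 72-hour collection for 1.2.6 or for the 72-hour parts of 1.2.5 and 1.2.8, and no contact after discharge names apnea. The clocks differ by about d hours, which is 4 to 24 hours if the assumed range is right.

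Whether data would actually be lost depends on the POD 3 survey, which cannot be seen. If it lacks the items, those questions have no data source at the requested time. If it has them, what remains is to list them and align the timing. The change should be made in either case. The primary comparison and its sample size, the section 3.2 aims and the in-hospital parts of 1.2.5 and 1.2.8 do not depend on it.

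**What to change.** In section 5.3, for all randomized children, put four items on the existing POD 3 survey, or list them if they are already there:

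- a parent pain score on a named scale;
- nausea, yes or no;
- number of vomiting episodes;
- number of witnessed apneas.

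Give the items a fixed recall period, for example since discharge.

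Use one clock across 1.2.5, 1.2.6, 1.2.8 and 5.3. Either send the survey 72 hours after discharge, or reword the three questions to POD 3. The first gives every child the same 72 hours at home. The second is simpler to run but leaves about 72 − d hours since discharge, which varies between children and should be acknowledged.

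Report in-hospital and post-discharge counts separately. Question 1.2.5 names both periods, and a merged count could hide a difference confined to home or count events twice.

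The cost is a few items on a survey already being sent, wording changes in 5.3 and, if that option is chosen, in three questions, and slightly more caregiver burden. Randomization and sample size do not change.
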